6.6.3.4 Survivability from Time of Index Procedure to Death

Overall survival is defined as (date of death due to any cause or date of last contact – date of surgery). A Kaplan-Meier plot for overall survival will be presented. Subjects will be censored based on their last date in the study if the event of death is not identified.

6.7 Safety Endpoints and Analyses

All safety endpoints will be summarized for ITT population. The safety endpoints will be evaluated through Day 90 and for the extended follow up portion of the trial at Days 180 and 360.

6.7.1.1 Safety Success (Clinical and Radiographic)

Safety Success is evaluated according to a composite endpoint by meeting all of the following criteria:

- Clinical
 - No Serious Device Related Complications
 - No additional surgical interventions:
 - Revisions, supplements, fixations, or removals

If subject does not have device related SAE or no reoperation CRF page filled, he/she can be considered as clinical success, meeting both criteria: “No Serious Device Related Complications” and “No additional surgical interventions: Revisions, supplements, fixations, or removals”.

- Radiographic
 - No device fracture, migrations, mal-alignment or loss of reduction or fixation

If subject does not have device malfunction (fracture, migration, other) recorded on the CRF, subject can be considered as radiographic success, meeting radiographic criteria.

Subject achieves safety success if subject meets both clinical and radiographic success. The number and percentage of subjects achieving the safety success endpoint will be reported cumulatively at Day 7-14, Day 30, and Day 90, as well as at each of the extended follow up periods and with 95% 2-sided exact binomial confidence intervals. Only evaluable subjects will be included in the summary at each time point. Evaluable subject is defined as subject staying in the study long enough to reach the time point.

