Version 2.0: 25 March 2016	
Clarified analysis of primary endpointClarified Enrolled subject to be consistent with protocolClarified DBL and CSR activities at all patients complete Day 90 visits, and another DBL and CSR extension by the end of studyClarified analyses will be conducted at two DBL timepointsRemoved missing data convention for incomplete diagnosis or treatment dateRemoved missing date imputation for AE and CM dateRemoved prior medication from prior/concomitant medicationAdded summary for % change of VAS values from baseline to Day 90 visit
Version 3.0: 18OCT 2016	
Clarify baseline definition, added baseline definition for ROM in Section 4.2.Clarify that only subjects with non-missing baseline and any post baseline values will be included in the analysis in Section 6.6.1.Clarify Safety success in 6.7.1.1. Radiographic success will be determined by examining device malfunction, device fracture, device removal recorded on CRF. Safety success will be determined by composite criteria on clinical and radiographic success. Statistical review meeting is removed from the text. Defined evaluable subjects in the safety summary.Clarify ranges for ROM tests, added percent change from baseline for summary.Added new analysis comparing mean VAS change from baseline at 90 Day F/U between subjects with actual and impending fracture in section 6.6.1.4

	
• Summaries for disability status and return to work status have been removed due to sponsor request
Version 3.1: 15NOV 2016	
• Removed “as the date of data extraction” from the definition of evaluable subject in safety success analysis in section 6.7.1.1.

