6.6.2 Secondary Effectiveness Endpoints and Analyses

6.6.2.1 Procedure- and Device-related Complication Rate

When there is device performance issue/Malfunction, the date and time period when issue occurred will be recorded on CRF. Time period can be “During device preparation”, “During device implantation”, or “Post-Implantation”. Date/Time, time period, and specific reason on device malfunction will be listed. The number and percentage of subjects who experience a procedure- or device-related complication by the day 90 visit will be presented along with the corresponding 95% binomial confidence interval. Subjects with more than one device malfunction will be counted only once. The percentage of subjects who experience the complications by the day 180 and 360 visits will also be summarized.

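### Safety Success at Day 90 leaves recorded failures who exit early out of its denominator and does not separate subjects without a film from subjects with a clean one

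*SAP*

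**What the plan says.** Safety Success stands under the Primary Endpoint heading of the protocol (Synopsis and 6.1.1). It is a composite of a clinical and a radiographic part, reported at Day 7-14, 30, 90, 180 and 360 with exact 95% intervals. The radiographic criterion, the same in both documents, is "No device fracture, migrations, mal-alignment or loss of reduction or fixation".

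SAP 6.7.1.1 makes this operational as follows:

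- Radiographic part: "If subject does not have device malfunction (fracture, migration, other) recorded on the CRF, subject can be considered as radiographic success".
- Denominator: "Only evaluable subjects will be included in the summary at each time point".
- Meaning of evaluable: "Evaluable subject is defined as subject staying in the study long enough to reach the time point".

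The SAP revision history for version 3.0 announces the CRF-based approach: "Radiographic success will be determined by examining device malfunction, device fracture, device removal recorded on CRF". On the malfunction form, SAP 6.6.2.1 says "the date and time period when issue occurred will be recorded on CRF". The periods are "During device preparation", implantation and post-implantation, and the specific reason is to be listed. Section 7.0 says that missing safety data are not replaced. Films are scheduled at every follow-up visit (protocol 8.3.1 to 8.3.3).

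**The concern.** A cumulative rate should carry a failure forward once it has happened. Here the time-in-study condition is applied afresh at each time point, so a failure before Day 90 counts at Day 90 only if the subject is still present. In metastatic bone disease, early exit through death or decline is expected. The plan allows for 15% premature withdrawal (SAP 3.5) and selects 37 patients in order to have 30 evaluable at the interim analysis (SAP 8.0).

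The radiographic rule tests whether a form entry exists, not whether a film was taken and read. Section 7.0 says missing safety data are not replaced, yet an absent film has in effect the same result as a clean one, and nothing in the derivation tells the two apart.

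At stake is the trial's composite safety proportion, in a study meant to support marketing clearance.

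**Working it through.** Neither document gives a rate, goal or sample size for Safety Success, so there is no planned figure to reproduce. The check applies the rule to four kinds of subject and then illustrates the size.

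**Applying the SAP rule at Day 90**

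1. Recorded failure on Day 40, death on Day 70: did not reach Day 90, so not evaluable and absent from numerator and denominator.
2. In the study at Day 90, film read as clean, no entry: success.
3. In the study at Day 90, no film, no entry: evaluable on time alone, so radiographic success. Same result as case 2.
4. Mal-alignment seen on film: counts against radiographic success only if entered as a malfunction under *other*. Protocol 13.1 G defines device fracture and clinically significant migration, but not mal-alignment or loss of reduction or fixation. Neither document defines *other*.

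**Inputs for the illustration**

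- Planned enrolment 80 and 15% withdrawal (SAP 3.5): 80 × 0.15 = 12 leave, 68 remain. The 68 is a number evaluable for VAS. Safety Success uses time in study, so the true n may differ.
- Assumed: no recorded failure among those who stay. The numbers of early failures (f) and missing films (m) are also assumed.
- Interval: exact binomial (Clopper-Pearson), 95% two-sided, as the SAP specifies. With x = n the lower limit is 0.025^(1/n). For n = 68 it is 0.025^(1/68) = 94.7%.

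**Early failures who leave before Day 90** (SAP: 68/68; retained: 68/(68 + f))

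| f | SAP rule | Failures retained |
|---|---|---|
| 1 | 100% (94.7 to 100) | 68/69 = 98.6% (92.2 to 100) |
| 2 | 100% (94.7 to 100) | 68/70 = 97.1% (90.1 to 99.7) |
| 3 | 100% (94.7 to 100) | 68/71 = 95.8% (88.1 to 99.1) |

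**Subjects in the study without a film** (excluded: (n − m)/(n − m); as failures: (n − m)/n)

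| n, m | SAP rule | Excluded | Counted as failures (bound) |
|---|---|---|---|
| 68, 3 | 100% (94.7 to 100) | 65/65 = 100% (94.5 to 100) | 65/68 = 95.6% (87.6 to 99.1) |
| 68, 7 | 100% (94.7 to 100) | 61/61 = 100% (94.1 to 100) | 61/68 = 89.7% (79.9 to 95.8) |
| 60, 7 | 100% (94.0 to 100) | 53/53 = 100% (93.3 to 100) | 53/60 = 88.3% (77.4 to 95.2) |
| 80, 7 | 100% (95.5 to 100) | 73/73 = 100% (95.1 to 100) | 73/80 = 91.3% (82.8 to 96.4) |

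With seven films missing out of 68, exclusion lowers the lower limit by 94.7 − 94.1 = 0.6 point and leaves the rate at 100%. The 89.7% is an extreme bound, not an estimate.

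**The case against.** **Early failures are not lost from the report.** They appear at time points the subject did reach, in the complication rate by Day 90 on the ITT population, and in the cumulative adverse event tables. This stands. The distortion is confined to the composite percentage at the later time point.

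**The rule is event-based, and missing films are traceable.** Protocol 10.8.3 requires missed assessments to be justified on the Protocol Deviation CRF, and SAP 6.2 summarises deviations by visit and type. A later film may also reveal an earlier event. So the claim cannot be that missing films are invisible. It is that the derivation ignores them, and a film-only finding that is never entered stays a success.

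**Two components may be fully captured.** A reader might infer that mal-alignment and loss of reduction or fixation were dropped. The documents do not support that: *other* is in the rule, the specific reason is listed, and the annotated CRF that may define the category is not available. One that led to a device-related SAE or a reoperation would also fail the clinical part. What remains is an undefined word.

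**Pre-implantation malfunctions need not count.** A reader might infer that an entry during preparation fails a subject. The rule says only that no entry allows success. It does not say that every entry is a failure, and the criterion above it would not fail such a subject. This is an ambiguity to settle.

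Nor was the rule concealed: the revision history states it.

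**Conclusion.** The concern holds in two respects, both read directly from SAP 6.7.1.1. Recorded failures who exit before a time point leave that time point's denominator, which raises the reported rate. Unassessed subjects and subjects with a clean film are scored alike. Two ambiguities go with them: what *other* covers, and whether entries from preparation or implantation count against radiographic success.

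The size is unknown. On the assumed counts, one to three early failures who leave move 100% to between 98.6% and 95.8%. Excluding unassessed subjects alone changes little, and only the bound that counts them as failures is large.

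A reader might conclude that the trial's error rate or power is affected, or that the radiographic rate is certainly inflated. Neither follows. The endpoint has no hypothesis or performance goal, and if pre-implantation entries were counted as failures the error would run the other way, so the net direction across all the issues cannot be signed.

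The clinical sentence, "If subject does not have device related SAE or no reoperation CRF page filled, he/she can be considered as clinical success, meeting both criteria", might be read as letting either condition suffice. Its closing words show that both were meant, so this is a wording correction only. The point should be fixed, but it does not threaten the primary effectiveness tests.

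**What to change.** Amend SAP 6.7.1.1:

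- **Failures.** Count any failure on or before the time point as a failure and keep that subject in the denominator, whatever happens later. State openly that event-free early exits remain outside the rate, so that it leans towards failure.
- **Unassessed subjects.** Classify a subject with no prior failure and no assessed film at or after the time point as not assessable. Report that number and add one sensitivity analysis counting these subjects as failures.
- **Entries that count.** Use only post-implantation malfunction entries for radiographic success. State that *other* includes mal-alignment and loss of reduction or fixation, and use film assessments where they are already recorded. If they are not recorded by component, say so.
- **Wording.** Replace *or* with *and* in the clinical sentence.

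The cost is SAP wording, derivation code and one sensitivity table. No new visits, films or readings are needed. Some subjects may become not assessable and the reported rate may be somewhat lower.

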#### **6.1.1 Primary Endpoint**

Pain Reduction

- Change in VAS Pain Score at Day 90

Functional Improvement

- Change in Revised Musculoskeletal Tumor Society Rating Scale for Upper Extremity (MSTS) at Day 90

Primary effectiveness will be evaluated relative to literature-based historical controls. These were selected on the basis of comparability to the target population and similarity to the investigational device. There are two primary effectiveness endpoints, reduction in pain at 90 days relative to pre-treatment baseline and improvement in function at 90 days relative to pre-treatment baseline. The changes in VAS pain and MSTS from pre-treatment baseline to day 90 will be involved in the primary effectiveness tests to be applied to enrolled patients who have actual or impending fractures, with VAS pain scores of at least 60mm. Non-inferiority of mean changes over time will be compared relative to reference values determined through evaluation of historical controls. Testing for VAS pain reduction will first be performed. Only if the null hypothesis of inferiority in mean VAS pain improvement is rejected at  $p<0.05$ , will the co-primary endpoint MSTS be similarly tested.

Safety Success is evaluated according to a composite endpoint by meeting all of the following criteria:

- Clinical
  - No Serious Device Related Complications
  - No additional surgical interventions:

- Revisions, supplements, fixations, or removals
- Radiographic
  - No device fracture, migrations, mal-alignment or loss of reduction or fixation

The number and percentage of patients achieving the Safety Success endpoint will be reported cumulatively for day 7-14, 30, and 90 and 180 and 360 and with 95% 2-sided exact binomial confidence intervals.

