## **9.3 Reporting to Sponsor**

All AEs classified as SAEs, or UADEs shall be reported by the PI (or designee) to the study CRO via [contact] or email ([contact]) within 24 hours of learning of the AE.

The PI (or designee) shall send a written report, including a narrative description of the SAE/UADE, to the Sponsor or CRO, within 3 working days of the initial report.

Subject death during the study must be reported by the PI (or designee) with written documentation by facsimile to the Sponsor or CRO within 24 hours of the PI's knowledge of the death. Notification of death must include a brief statement of the relevant details of the death and is required to be signed by the investigator. A copy of the death records, death certificates, and an autopsy report (if performed) should be sent to the Sponsor or the Sponsor's authorized representative (CRO) within 10 days post-autopsy.

In the event of death, efforts should be made to perform an autopsy in order to assess the state of the target arm. If autopsy is not performed, written documentation from the PI will be required regarding the reasons why.

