#### G. Device Specific Definitions

**Clinically Significant Device Migration:** Change in bone pin position compared to immediate post-deployment position greater than 1cm (either proximal or distal) as documented by radiographic imaging and associated with clinical symptoms.

**Device Fracture:** Any loss of structural integrity (i.e. breakage or separation) of the implanted, polymerized bone pin. Documented by imaging or visually confirmed at the time of surgery or autopsy.

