3.5 Sample Size Justification

Approximately 80 subjects will be enrolled into this study. The following text will give sample size justification details.

VAS pain improvement: The primary endpoint is change in VAS from baseline to Day 90. All patients will be included in the primary analysis of this endpoint through the use of a mixed model repeated measures (MMRM) model assuming an unstructured covariance matrix. To be conservative, statistical power is evaluated on the basis of a single-sample t-test with a 1-sided alpha=0.05 based on the change at Day 90. The null and alternative hypotheses of interest are:

$$H_0: \text{mean improvement in VAS at Day 90} \leq 53.8$$

$$H_a: \text{mean improvement in VAS at Day 90} > 53.8$$

Based on the historical control data in protocol Section 6.3, an estimate of the standard deviation of the primary endpoint is 13.3. Under the assumption this is the true standard deviation, under the assumption the true mean improvement from baseline VAS at Day 90 is 58, then 68 evaluable patients yields over 80% power to reject the null hypothesis in favor of the alternative. In order to account for 15% premature withdrawal rate, a total of 80 patients will be enrolled. Note that the assumption of 58 for the true mean improvement from baseline VAS at 90 days may be conservative given the historical control data in protocol Section 6.3 (where the overall mean change, or reference value, was estimated to be approximately 67, over a shorter period than 90 days).

MSTS improvement: The second primary endpoint, to be tested if the above null hypothesis for improvement in VAS is rejected, is change in MSTS from baseline at Day 90; this will be analyzed a similar MMRM manner as the primary endpoint above. The null and alternative hypotheses of interest for this endpoint are:

$$H_0: \text{mean improvement in MSTS at Day 90} \leq 23.7$$

$$H_a: \text{mean improvement in MSTS at Day 90} > 23.7$$

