6.7.1.2 Adverse Events (AEs)

Adverse events (AEs) will be collected from the time of surgery until the last study visit or premature discontinuation from the study.

Treatment-emergent adverse events (TEAEs) are those AEs which worsen in severity on or after date of surgery or with onset date on or after date of surgery. AEs with missing start dates, but with stop dates either overlapping into the treatment period or missing, will be considered TEAEs. Treatment-related includes possibly or probably or definitely relationship of the event to the investigational device, procedure, anesthesia, or oncology medicine.

All AEs will be coded by System Organ Class (SOC) and Preferred Term (PT) using the Medical Dictionary for Regulatory Activities (MedDRA). Incidences of TEAEs will be tabulated by SOC and PT, cumulatively per time point (Up to Day 90, Up to Day 180, and Up to Day 360). Incidences of TEAEs will also be presented by maximum severity, seriousness, unanticipated adverse device effect (UADE) and relatedness (device or procedure related) cumulatively per time point. This includes the reporting of device revisions, reoperations, removals, supplemental fixations, or other procedures. Subjects who discontinued due to TEAEs will be summarized by SOC and PT in a separate table. Patients are counted only once in each SOC, and only once in each PT category, cumulatively per time point.

The following tables will be developed for summarizing AEs cumulatively per time point.

- Overall summary of TEAEs, it includes number of treatment-emergent adverse events, subjects with any TEAE, subjects with any serious adverse events (SAE), subjects with any severe TEAEs, subjects with any device related TEAEs, subjects with any procedure related TEAEs, subjects with any anesthesia related TEAEs, subjects with any Oncology Medicine related TEAEs, subjects with any unanticipated adverse device effect (UADE), subjects with TEAEs leading to study discontinuation and death.
- Summary of TEAEs by system organ class and preferred terms
- Summary of serious TEAEs by system organ class and preferred terms
- Summary of TEAEs by system organ class, preferred terms and maximum severity

- Summary of treatment-related TEAEs by system organ class, preferred terms (device related, procedure related, anesthesia related and oncology medicine related).
- Summary of unanticipated adverse device effect (UADE) by system organ class and preferred terms

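### Safety Success is reported as cumulative, but a subject who fails and then dies or withdraws drops out of every later row

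*SAP*

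**What the plan says.** Protocol 6.1.1 lists Safety Success, a clinical and radiographic composite, under the primary endpoint: "The number and percentage of patients achieving the Safety Success endpoint will be reported cumulatively", at Days 7-14, 30, 90, 180 and 360, with exact 95% confidence intervals. It does not restrict who enters each row.

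SAP 6.7.1.1 keeps the cumulative reporting and adds a restriction: "Only evaluable subjects will be included in the summary at each time point". It then defines the term: "Evaluable subject is defined as subject staying in the study long enough to reach the time point". Neither that section nor SAP 7.0 on missing values makes an exception for a failure recorded before the subject left.

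The next subsection, SAP 6.7.1.2, has no such restriction: "Incidences of TEAEs will be tabulated by SOC and PT, cumulatively per time point".

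The SAP revision history mentions the rule for version 3.0 ("Defined evaluable subjects in the safety summary"). It is not among the ten changes from the protocol in SAP Section 9.

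**The concern.** A failure, once recorded, is known at every later date, and later follow-up cannot undo it. A cumulative row that drops it because the subject has since left discards observed data. If failure and exit both fall between two time points, the subject may count as a success in the earlier row and never counts as a failure.

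The documents allow for this sequence. Protocol 9.1 makes death one of the criteria for a serious event. Protocol 9.3 says: "In the event of death, efforts should be made to perform an autopsy in order to assess the state of the target arm". The device-fracture definition in Protocol 13.1 G reads: "Documented by imaging or visually confirmed at the time of surgery or autopsy". A fracture found at autopsy belongs to a subject who cannot reach the next time point, so the composite leaves out a failure that sites are asked to look for.

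What is at stake is the reported percentage and its interval for a composite placed under the primary endpoint, and its agreement with the adverse event tables. No hypothesis test is affected.

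**Working it through.** **1. The plan's own attrition figure.** SAP 3.5: "In order to account for 15% premature withdrawal rate, a total of 80 patients will be enrolled". Check: 68 / (1 − 0.15) = 80. This reproduces, and 15% is used below as exit by Day 90. The documents give no failure rate, no ratio of exit after failure to exit before it, and no retention figure for Day 360. Those inputs are assumptions.

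**2. The rate can rise (illustrative counts).**
- Day 30: 80 treated, 8 failures, all still in the study: 72/80 = 90.0% (exact 95% CI 81.2 to 95.6).
- By Day 90: one more failure (9 in all) and 12 exits, 3 of them failures. Of the 68 remaining, 6 have failed: 62/68 = 91.2% (81.8 to 96.7).
- With recorded failures kept: 62/(68 + 3) = 62/71 = 87.3% (77.3 to 94.0).

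Failures rise from 8 to 9, yet reported success rises by 1.2 points. If the 12 leavers are a random draw from the 80, the chance of 3 or more failures among them is 13% (hypergeometric), so the example is possible but not typical.

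**3. Expected size.** Take constant hazards over one follow-up interval, with failure probability F and event-free exit probability X:
- λ = −ln(1 − F) and μ = −ln(1 − X). After failure the exit hazard is rμ.
- Event-free and in study: E = (1 − F)(1 − X).
- Failed and still in study: S = λ[exp(−rμ) − exp(−λ − μ)] / (λ + μ − rμ).
- Failure recorded, in study or not: R = λ/(λ + μ) × [1 − E].
- SAP rule = E/(E + S). Failures carried forward = E/(E + R). Share of recorded failures missing from the row = (R − S)/R.

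For F = 0.10 and X = 0.15: λ = 0.1054, μ = 0.1625, E = 0.765, R = 0.3933 × 0.235 = 0.0924.

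| r | S | SAP rule | Error against 90.0% | Recorded failures missing |
|---|---|---|---|---|
| 0.5 | 0.0886 | 89.6% | −0.4 | 4% |
| 1 | 0.0850 | 90.0% | 0 | 8% |
| 3 | 0.0724 | 91.4% | +1.4 | 22% |
| 5 | 0.0621 | 92.5% | +2.5 | 33% |

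At r = 3 to 5 the overstatement is 0.7 to 1.3 points if F is 5%, and 2.0 to 3.6 if F is 15%. For Day 360 with F = 10%, the SAP rule shows 92.7% to 94.5% at an assumed 30% exit and 94.4% to 96.5% at an assumed 50% exit (r = 3 to 5). It still shows 90.0% at r = 1.

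**4. The carried-forward rate has its own bias.** It is 0.765/(0.765 + 0.0924) = 89.2% at 15% exit, whatever r is. At 50% exit, E = 0.45 and R = 0.0726, which gives 86.1%. If exit is unrelated to failure, both are too low against 90.0%.

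**5. The benchmark depends on the estimand.** 90.0% is success as if nobody left. If every exit were a death and event-free death is a competing event, the target is 1 − R: 90.8% at 15% exit and 92.7% at 50%. Against that target the SAP rule at r = 3 overstates by 0.6 and 1.7 points (91.4% and 94.4%).

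**The case against.** The strongest reply is that the SAP percentage is unbiased when exit is unrelated to failure, whereas carrying failures forward is then biased downward. With 10% failure, the SAP rule's overstatement exceeds the carried-forward understatement only when failed subjects leave about 2.1 times as fast (15% exit) or 2.7 times as fast (50% exit). No passage supports such a ratio. Some point the other way: Protocol 9.1 has unresolved serious events followed up, Protocol 10.6 requires X-rays before and after device removal, and Protocol 6.4.2.1 does not make failure a ground for exit. All of this stands. It rules out a carried-forward rate as the only display, but it does not justify deleting recorded failures from a row labelled cumulative.

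It is also true that no test or performance goal is attached. The Day 90 effect of 1.4 to 2.5 points is small beside an interval about 14 points wide. The autopsy wording shows that the sequence is foreseen, not that it is frequent.

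Four stronger readings are tempting, and the documents do not support them:
- That the rule always flatters the device. The direction depends on an unknown exit ratio.
- That failures vanish from the report. They remain in the adverse event tables and listings (SAP 6.7.1.2) and the complication rate (SAP 6.6.2.1).
- That an evaluable subset contradicts the ITT statement in SAP 6.7. Some rule is needed for subjects not yet due, because SAP 4.1 issues the first report while follow-up continues.
- That the carried-forward rate and an all-ITT rate by recorded status bracket the truth. If event-free leavers would have failed more often than those observed, the truth lies below both.

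**Conclusion.** The gap in the text is certain: SAP 6.7.1.1 has no clause that keeps a recorded failure, and no other section supplies one. Followed literally, the rule lets the cumulative rate rise as failures accumulate and lets the composite disagree with the adverse event tables.

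The direction and size of any bias are not established. The figures rest on assumed failure rates and exit ratios, constant hazards and, for Day 360, assumed retention. Some recorded failures are missing from the row even when the percentage itself is unbiased. For a descriptive endpoint whose events are reported elsewhere, this is a minor to moderate point. It is worth fixing before the tables are produced, because the data are already planned for collection.

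**What to change.** Replace the last sentence of SAP 6.7.1.1 with:

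> A subject is evaluable at a time point if the subject stayed in the study to reach it or had a Safety Success failure recorded on or before it (including one found at autopsy). A recorded failure counts at that and every later time point that has fallen due.

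Keep the number, percentage and exact 95% interval. Because this version understates success when exit is unrelated to failure, add three things:
- Beside it, at equal standing, show the cumulative incidence of first failure in ITT, with event-free death as a competing event and other event-free subjects censored at exit or at the data cut.
- At each time point, footnote the number of recorded failures among subjects who did not reach it.
- List the evaluable rule in SAP Section 9 as a change from the protocol.

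Do not describe the crude rates as bracketing the truth.

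The cost is a short SAP edit and modest programming, including the competing-risk display. No new data are needed. The reported rate may be slightly less favourable.
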